The difference in treatment success between G-POEM and sham groups at 6 months is the only confirmatory hypothesis test of the study and the 5% p-value threshold for statistical significance will be applied. All the other hypotheses and secondary outcomes are considered exploratory and p-values from the corresponding tests will be presented without any multiple testing correction without the aim to keep the overall false positive error rate at 5% across all results.

Baseline characteristics will be compared only using descriptive statistics as any potential statistically significant difference between the two study groups would be due to chance by design in a randomized trial.

An interim-analysis will be performed when 40% of patients will have completed the 6 months follow-up. The interim analysis will be performed on available data basis investigating the primary hypothesis with the same tools as planned for the final analysis. Since no rules for interim stopping of the trial based on adjusted thresholds for p-values was specified in the study design, the Haybittle–Peto boundary will be used for potential stopping of the trial for early confirmation of the treatment effect. On the other hand, enrollment would be stopped for futility if the interim conditional power of the study assuming the observed effect sizes for the remaining patients was below 20%. Also, analysis of adverse events could result in study termination.

13. Study monitoring, data and safety monitoring board

The study will be monitored by an independent certified agency (to check for reliability of data and ethical standards). A standard Data and Safety Monitoring Board (DSMB) will be created in the coordinating centre in Prague and its membership will include: 4 gastroenterologists, 1 independent specialist (MD), 1 statistician, 1 lawyer and 1 independent person (not MD). The main aim of DSMB will be: to review the research protocols, informed consent documents, and plans for data and safety monitoring, including all proposed revisions; to evaluate the progress of studies, including periodic assessments of data quality and timeliness, participant recruitment; to protect the safety of the study participants; to report on the safety of the study participants and progress of the trial; to consider factors external to the study when relevant information becomes available, such as scientific or therapeutic

developments that may have an impact on the safety of the participants or the ethics of the study; to make recommendations.

14. Study termination

Individual case:

- Severe peri-procedural complications as bleedings or perforations requiring a surgical intervention.
- Technically unsuccessful/unfinished G-POEM.
- *The patient's request to terminate the participation in the study.*
- Severe symptomatology requiring intervention not allowing to finish 6 months of the follow up, especially in patients in the sham group (pyloric botulinum toxin injection, balloon dilatation, laparoscopic surgery, transpyloric stenting).

15. Ethical and administrative aspects

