6.3.3. Post-randomization tests (before the procedure)

- PAGI QoL (appendix 4)
- Body weight/BMI, ASA physical status
- Current lab values (Haemoglobin, WBC, RBC, Thrombocytes, CRP, Quick, Haemoglobin A1c in patients with DM)
- Upper GI endoscopy 1 day prior to the procedure (optional for removing food residues)
- EndoFLIP measurement of pyloric distensibility, cross-sectional area and diameter
 under general anesthesia before G-POEM/sham

Patients will be admitted to the hospital one day prior to the procedure or the day of the procedure. The day before the procedure, patients will be allowed to drink until 20.00. In the morning (day of the procedure), proton pump inhibitor (PPI) (e.g. omeprazole 40 mg) will be administered intravenously to patients allocated to the active (G-POEM) group; patients in the sham arm will be given placebo (normal saline) (**Appendix 5**).

7. EndoFLIP

EndoFLIP (= Functional Lumen Imaging Probe) is a new method using a principle of impedance planimetry allowing to measure distensibility of a hollow organ, ideally sphincter. In the stomach, it could help to understand the contributing pathophysiology of an impaired function of a pyloric sphincter in patients with gastroparesis. Furthermore, it could help to select appropriate patients for pylorus-directed therapies in patients with gastroparesis, as EndoFLIP provides real-time and dynamic information on pyloric distention, cross-sectional area and diameter.

EndoFLIP measurement will be performed three times: before the procedure (during sham procedure or just before G-POEM), immediately after G-POEM and 3-9 months after G-POEM, always in sedated patients (3-9 months) or in patients under general anesthesia (prior to and after G-POEM). After the calibration, the balloon, equipped with pressure and impedance sensors, will be introduced into the esophagus and under endoscopic control will be passed through the pylorus into the correct position. If necessary, special accessories (snare, grasper) will be used. After that, measurement of various parameters will be performed and the following values will be recorded: distensibility, balloon pressure, cross sectional area, diameter under different balloon volumes (30, 40 and 50 mL). EndoFLIP procedure prolongs the endoscopic examination by approximately 10-15 minutes.

G-POEM procedure

The procedure consists of the following steps (Table 5):

Table 5:

- 1) Mucosal incision at the greater curvature 3-5 cm from the pylorus

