- 2) Submucosal tunnelling
- 3) Finding pyloric sphincter
- 4) Myotomy (2-3 cm) of the pyloric muscle
- 5) Incision closure (endoclips or suture device)

All procedures will be performed by an experienced endoscopist under general anaesthesia with a high-definition endoscope, fitted with a plastic distal attachment. Exclusively CO² will be used for insufflation. Submucosal tunnel will be created by choosing an entry point (usually at 5-6 o'clock) in the antrum at the greater curvature approximately 3-5 cm proximal to the pylorus. After a mucosal incision (1-2 cm), a submucosal tunnel towards pyloric muscle will be created. After finding pyloric arc, the muscle will be myotomised (at 6 o'clock position, complete myotomy to the serosa, length 2-3 cm). For the whole procedure, TT knife or IT knife (Olympus) will be used. For mucosal incision, endocut mode will be used; for tunnelling and myotomy, spray or swift coagulation will be used. Coag-grasper will be used for haemostasis. At the end of the procedure, the mucosal incision will be closed by using endoclips, alternatively, suturing device (Apollo[®] OverStitch), OTSC clip or KING closure (endoloop + clips) may be used at the direction of an investigator. Inadvertent mucosal injuries will be closed by endoclips if necessary. All procedure-related instruments are listed in Table 6.

Table 6: G-POEM baseline instruments

Erbe Vio 300D with presets:

Endocut Q, Spray Coagulation 40-60W, Effect 2 (incision, dissection and myotomy) or Swift Coagulation.

Endocut I, Spray or Forced Coagulation 40W, Effect 2 (bleeding control with coag grasper)

CO₂ Unit, low flow CO₂

Waterjet pump with sterile fluid for flushing

High definition endoscope

Single use endotherapeutic instruments:

- IT and/or TT knife (with jet function if available)
- Coagrasper for haemostasis
- Injector
- Clips or endoscopic suturing device or endo-loop device or OVESCO clip
- e.g. MH-588 distal attachment (Olympus or Fuji)

Experienced endoscopist to be eligible to perform G-POEM in this study:

- At least 4 G-POEMs and one of following (Table 7)

Table 7:

- A) >35 POEMs or
- B) >30 ESD procedures

8. SHAM procedure

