Patients randomized into the sham group will undergo general anaesthesia (or deep sedation with propofol) and a standard upper GI endoscopy with a high definition endoscope will be performed. EndoFLIP measurement will be performed during the sham procedure. No G-POEM will be effectuated and patient will be awakened after 30-60 minutes. All other post-procedure tests will be done in the same fashion as in patients with G-POEM arm.

All "trialists" including the "paramedics" staff will be asked not to inform the patient about the treatment allocation.

9. Perioperative and post-operative management and follow-up

a. Perioperative management

- Sixty to fifteen minutes before the procedure, the patients (active group) will be administered antibiotics i.v.: Ceftriaxone 2 gr (or similar antibiotics) plus Metronidazole 500 mg. Patients in the sham group will be given placebo (normal saline).
- If necessary, pneumoperitoneum will be decompressed by using a Verres needle or venous cannula.

b. Postoperative management - day of the procedure:

- Recovery from general anaesthesia/sedation
- Analgesic and anti-emetic as needed
- i.v. omeprazole 3x40 mg (or other IPP) only in active arm, placebo (normal saline) in the sham arm
- Nothing per mouth until POD 1 (both arms)
- Thorough monitoring until POD 1

c. Post-operative day 1 (POD 1):

- Morning: last dose of i.v. omeprazole 40 mg i.v. (or similar PPI) placebo in the sham group. Then esomeprazole 2x40 mg (or other PPI) for at least 3 weeks (both arms).
- Ceftriaxone 2 gr i.v. or similar ATB, placebo in sham arm
- Blood (Haemoglobin, RBC, WBC, CRP, etc.)
- Mucosal integrity will be confirmed with either endoscopy or X-ray with water soluble contrast or both at the discretion of an investigator. If necessary, additional intervention to close mucosal incision will be used.
- If no leak is detected, patients will be allowed to drink clear fluids and begin realimentation.
- Discharge possible on POD 1 (or POD 2)

d. Follow-up visits:

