- 1. It would be highly unlikely that during the further course of the study, the results would change qualitatively. The p-value of the logistic regression analysis comparing the treatment success between G-POEM and sham groups is equal to p=0.003. Since no interim stopping scheme with pre-specified corrected alpha thresholds was specified, we primarily consider the Haybittle–Peto boundary. This boundary states the critical value of p=0.001 at all interim analyses and sometimes p=0.002 is used if only one interim analysis is performed. Our obtained p-value does not directly reach this level of significance, but taking into account the heuristic nature of the Haybittle–Peto approach and the fact that this approach is considered very conservative for stopping a trial, we believe that the evidence in favor of G-POEM efficacy is sufficient for stopping further enrollment.
- Even if the strict statistical threshold for early trial termination is not met, ethical reasons should be considered. In particular, the risks related to general anesthesia in the sham procedure can not be further justified in the light of the current results. The Board consider it unethical to continue with study enrolment.

There should be further studies assessing the key question of how to select patients who will benefit from G-POEM, but we believe that there is no need for further inclusion of sham procedures.

Data and Safety Monitoring Committee members:

Chairperson:

MUDr. [name] – gastroenterologist

Head physician

MEDIENDO s.r.o.

[name]

MUDr. [name] – gastroenterologist

MUDr. [name] - hepatologist

MUDr. [name] – gastroenterologist and hepatologist

MUDr. [name] - neurologist, independent specialist

Mgr. [name] – statistician

MUC. [name] - medical student

JUDr. [name] - lawyer

In Prague, 8th of February 2021

MUDr. [name]

Head physician

MEDIENDO s.r.o.

[name]

[name]

Mediendo s.r.o.
Gastroenterologie, odb. 105
[name]
[name]

[contact]

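### The sham may be done under deep sedation, but G-POEM and the pre-procedure EndoFLIP in both arms are specified under general anaesthesia; the sections conflict and leave an avoidable route to unblinding

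*Protocol*

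**What the plan says.** Four places in the protocol bear on the type of anaesthesia at the index procedure.

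- **Section 8 (SHAM procedure):** "Patients randomized into the sham group will undergo general anaesthesia (or deep sedation with propofol"). The same section adds that "EndoFLIP measurement will be performed during the sham procedure".
- **G-POEM procedure (the text around Table 5, after section 7):** "All procedures will be performed by an experienced endoscopist under general anaesthesia". No sedation option is given.
- **Section 6.3.3 (tests after randomisation, before the procedure):** EndoFLIP is measured "under general anesthesia before G-POEM/sham", which names both arms.
- **Section 7 (EndoFLIP):** measurements are taken "always in sedated patients (3-9 months) or in patients under general anesthesia (prior to and after G-POEM"). Sedation is tied to the follow-up measurement only.

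The recovery item in section 9b, "Recovery from general anaesthesia/sedation", fits either type and does not settle the matter.

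On blinding, section 6.3.2 requires that patients not learn their assignment, section 8 asks staff not to disclose it, and section 9d plans disclosure at 6 months. The main outcome (section 10a) is at least a halving of the total GCSI at 6 months, scored by the patient.

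**The concern.** Section 8 permits something that section 6.3.3 rules out, so a site cannot follow both when it sedates a sham patient. Two consequences follow.

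**Blinding.** The option exists in the sham arm alone. The summary (section 3) says the sham is there to control for touch and belief, and the primary endpoint is a symptom score given by the patient. A procedural feature that can occur in only one arm works against that purpose.

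**EndoFLIP.** The sham-arm measurement is taken under whatever the sham uses. A note to Table 8B says it is not repeated before a cross-over G-POEM, so it stands as that patient's pre-treatment value. Section 12 also lists EndoFLIP among the candidate predictors of success. Values taken under two sets of conditions, linked to arm, would be mixed in those analyses.

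**Working it through.** The protocol gives no figure on this point, so the check is a comparison of the sections.

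**1. Is there a contradiction?**

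| Item | G-POEM arm | Sham arm |
|---|---|---|
| Procedure | General anaesthesia only (G-POEM procedure text) | General anaesthesia or propofol sedation (section 8) |
| Pre-procedure EndoFLIP, stated condition | General anaesthesia (6.3.3 and 7) | General anaesthesia (6.3.3) |
| Pre-procedure EndoFLIP, timing | Just before G-POEM (7) | During the sham (7 and 8) |

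In the sham arm, EndoFLIP takes place within the procedure. If the procedure is under sedation, so is the EndoFLIP, and 6.3.3 is not met. The statement that both arms are covered rests on 6.3.3; the bracket in section 7 names G-POEM only.

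**2. Can the type depend on the arm?** Randomisation (6.3.2) precedes the procedure, and the centre receives the allocation by e-mail. Section 8 gives no criterion for choosing. The type is therefore settled after the arm is known to the centre.

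**3. Can the type reveal the arm?** Under the protocol as written, the probability of sedation at the index procedure is 0 in the G-POEM arm and some unknown value from 0 to 1 in the sham arm. Knowing that sedation was used therefore identifies sham. Knowing that general anaesthesia was used does not identify either arm with certainty. For a patient to reach the inference, two things are needed: learning which type was used, and knowing that G-POEM is never done under sedation. Appendix 5 includes an anaesthesiologist's examination the day before, a natural occasion for the type to be discussed.

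**4. How large could the effect be?** The proportional loss of sham successes would be roughly the product of three quantities: the share of sham patients sedated, the share of those who infer their arm, and the share of their successes lost as a result. None of the three is given. The planned sham arm is 43 patients (section 11), so the number exposed lies anywhere from 0 to 43. No useful range for the bias follows.

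**5. Which EndoFLIP analyses are touched?**
- Before-and-after comparison in cross-over patients: the earlier value may be under sedation, while section 7 puts the value immediately after G-POEM under general anaesthesia.
- Predictor search (section 12): sham-arm values may come from a different condition.
- Change between arms (section 10.2, outcome 7): sham patients have only a sham EndoFLIP at 3 months (section 9d, Table 8B). That comparison is already limited for another reason.

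Section 12 declares everything beyond the 6-month primary test exploratory.

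**The case against.** The strongest reply is that unblinding is inferred, not shown. General anaesthesia is the first-named option for the sham, and sedation stands in brackets. The sedation is deep, the patient is woken after 30 to 60 minutes, and the protocol text at hand does not say what patients are told about anaesthesia. Other safeguards exist: saline in place of the intravenous PPI and antibiotics, fasting until the next day in both arms, a sham EndoFLIP at follow-up, and an instruction in Appendix 5 to keep patients and staff blinded. This stands as far as it goes: disclosure is possible, not certain. It does not remove the contradiction. The request not to disclose allocation does not cover a fact from which allocation can be deduced.

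Four stronger readings are tempting, and the documents do not support them.

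- *A sedated sham patient has been told the arm.* Both pieces of knowledge in step 3 are needed, and neither is documented.
- *The type I error is inflated by a stated amount.* Any such figure would apply an assumed shift to the sham arm without knowing how many were sedated.
- *The monitoring board's report proves the contradiction.* It mentions "the risks related to general anesthesia in the sham procedure", but it is a later report, not a rule of the plan. It suggests, if anything, that general anaesthesia was used in shams.
- *A between-arm comparison of baseline EndoFLIP is confounded.* No listed outcome makes that comparison.

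**Conclusion.** The point holds as an internal contradiction with a bearing on blinding. Section 8 cannot be followed under sedation without breaking 6.3.3, and it gives the sham arm alone an option that is chosen after randomisation without a stated rule. The risk to the patient-reported 6-month endpoint is real in kind, but its size cannot be computed from the documents. It is nil if no sham was sedated, or if no patient or carer could connect the type with the arm. The EndoFLIP consequence is confined to exploratory analyses, mainly the cross-over comparison and the predictor search. The conclusion assumes only that the sections mean what they say and that no selection rule exists elsewhere in the protocol. It takes no view on which form of anaesthesia is appropriate.

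**What to change.** 1. Reconcile section 6.3.3, section 7, the G-POEM procedure text and section 8 so that the type of anaesthesia neither depends on nor reveals the allocated arm. Which type or types to allow is for the clinical team.
2. Record the type given at each procedure on the CRF. For patients already treated, retrieve it from the anaesthesia record where possible.
3. If both types were used, report the number by arm and describe EndoFLIP values by type, including the sham values that serve as pre-G-POEM values in cross-over patients.

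The primary result should not be broken down by type. Type is set after randomisation and can differ by arm, and with 43 planned per arm such a split would be hard to interpret.

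The cost is protocol wording, one CRF field, and less freedom for sites in choosing anaesthesia for sham patients. That freedom may reflect a concern about anaesthesia risk, which the monitoring board's report itself raises for the sham arm; the clinical team has to weigh it.

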Follow up visits are scheduled at 3 and at 6 months. At 6 months, all patients will be informed about their treatment allocation and patients in the sham group will be offered G-POEM in case of their persisting symptomatology (no or minor benefit of the sham procedure). The decision must be made in next 3 months and these patients undergo the G-POEM procedure no longer than 6 months after the previous follow-up visit. Further follow-up visits for patients randomized to the active arm are scheduled at 12M, 24M and 36M.

Patients originally randomized into the sham arm, who will undergo G-POEM, will be followed like patients after G-POEM (f-u visits at 3M, 6M, 12M, 24M and 36M) (**Appendix 6**) except of scintigraphy/GEBT at 12M (Table 8B).

Patients originally randomized into the sham arm who had treatment success or didn't want to undergo G-POEM will be followed at 12M and 24M to be sure there is none treatment recurence.

For both, active and SHAM groups, diet modification, nutrition support, prokinetics, antiemetics are allowed during the follow-up. No interventions such as pyloric balloon dilatations, transpyloric stent placement, botox application or surgery) are allowed during the follow-up.

Unscheduled visits or telephone contacts may occur as needed. No time windows or minimum time separations are imposed for such visits or contacts. Data collection forms are not required at interim visits. If gastroparesis symptom exacerbation occurs between scheduled visits, complete the Interim Event Report (IE) form. The visit code for the form will be "n" (not applicable in this situation)

3M visit (±3 weeks):

- Symptom questionnaires (PAGI-QoL, GSCI, PAGI-SYM)
- Body weight/BMI
- Endoscopy
- Gastric emptying study (scintigraphy) in all pts
- Gastric emptying breath test (optional)
- EndoFLIP measurement (only after G-POEM, may be performed 3-9 months after G-POEM), patients from sham group will undergo the "sham EndoFLIP measurement"

6M visit (± 1 month):

- Symptom questionnaires (PAGI-QoL, GSCI, PAGI-SYM)
- Body weight/BMI

12M visit (± 1 month):

- Symptom questionnaires (PAGI-QoL, GSCI, PAGI-SYM)
- Body weight/BMI
- Endoscopy (optional)
- Gastric emptying study (scintigraphy) in the active arm only (Tab. 8A)
- Gastric emptying breath test (optional)
- No GES (scintigraphy) in the sham group after unblinded allocation to G-POEM (Tab. 8B)

24M and 36M visit (±2 months):

- Symptom questionnaires (PAGI-QoL, GSCI, PAGI-SYM)
- Body weight/BMI

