- Gastric emptying study (scintigraphy) at 36M (optional)

Table 8A – study design for patients in the active (G-POEM) group

		Patients in G-POEM group at the beginning of randomisation										
		Baseline	POD 0 – day of GPOEM	POD 1	3M	6M	12M	24M	36M			
Scinti / GE	BT	•			•	1	•		(optional)			
Endoscop	у	•	•	(optional)	•	-	(optional)					
GCSI + PA SYM + PA QoL	_	•			•	•	•	•	•			
Blood test	ts	•		•								
EndoFLIP			Before and after GPOEM		③							

GEBT (Gastric emptying breath test), QoL = Quality of Life, GCSI = Gastroparesis Cardinal Symptoms Index, PAGI-SYM = Patient Assessment of Upper Gastrointestinal Disorders Symptoms, PAGI-QoL = Patient Assessment of Upper Gastrointestinal Disorders-Quality of Life, POD - Post Operative Day.

Table 8B – study design for patients randomized in the sham group

		Patients in sham group / allocation to G-POEM procedure*											
	Baseli ne	POD 0	POD 1	3M	6M *	POD 0/ G-POEM	POD1	3M	6M	12M	24M	36M	
Scinti / GEBT	•			•	-			•				(optional	
Endoscopy	•	•	(optional)	•	-		(optional)	•		(optional)			
GCSI + PAGI-SYM + QoL, PAGI- QoL	•			•	•			•	•	•	•	•	
Blood tests	•		•				•						
EndoFLIP		⊕ Before [⊥]		Sham		After GPOEM		③					

^{*} At 6M, the patients in sham arm will be offered to undergo G-POEM (if their symptoms persist).

*In patients having undergone EndoFLIP during the sham procedure, no EndoFLIP measurement will be repeated prior to G-POEM.

♦ sham measurement

10. Study outcomes

a. Main outcome

Main outcome is the proportion of patients with treatment success at 6 months after the procedure.

Treatment success is defined as a decrease of a total GSCI symptom score at least **50%** (see Table 9 for GSCI values to define treatment success according to a baseline GSCI value).

Table 9: GSCI values to define treatment success according to the baseline GSCI value

Mean GCSI score total – baseline	Maximal GSCI score for treatment success (decrease of GSCI about 50%)
2.31*	1.15
2.4	1.20
2.5	1.25
2.6	1.30
2.7	1.35
2.8	1.40
2.9	1.45
3.0	1.50
3.1	1.55 (see description below the table)
3.2	1.60
3.3	1.65
3.4	1.70
3.5	1.75
3.6	1.80
3.7	1.85
3.8	1.90
3.9	1.95
4.0	2.00
4.1	2.05
4.2	2.10
4.3	2.15
4.4	2.20
4.5	2.25
4.6	2.30
4.7	2.35
4.8	2.40
4.9	2.45
5.0	2.50

NOTE: GSCI above 2.3 is an inclusion criterion

Example: If baseline GSCI value was 3.1, a patient will have treatment success if post-treatment GSCI score will be 1.55 or lower.

10.2. Secondary outcomes:

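### Needle decompression has no counterpart in the sham arm, and patients are never asked which treatment they believe they had, so masking of the patient-reported primary endpoint cannot be checked

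*Protocol*

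**What the plan says.** - **Endpoint and purpose of the sham.** Section 10a defines success as a fall of at least half in total GCSI, which the patient completes (Appendix 2). The statistical analysis plan within section 12 makes the 6-month comparison the only confirmatory test. The Study Summary gives control of touch and belief effects as the reason for using a sham.
- **Decompression.** Section 9a: "If necessary, pneumoperitoneum will be decompressed by using a Verres needle or venous cannula". No arm is named, and no mock puncture or dressing is described for sham patients.
- **Sham content.** Section 8 describes upper endoscopy with EndoFLIP under anaesthesia or deep sedation, then: "No G-POEM will be effectuated and patient will be awakened after 30-60 minutes". There is no tunnel and no myotomy.
- **Masking that is planned.** Saline replaces the intravenous PPI and antibiotics, both arms are kept nil by mouth, both receive oral PPI from POD 1, and sham patients have a sham EndoFLIP at 3 months. Section 8 adds that "staff will be asked not to inform the patient about the treatment allocation".
- **POD 1 testing.** Section 8: "All other post-procedure tests will be done in the same fashion as in patients with G-POEM arm". Section 9c: "Mucosal integrity will be confirmed with either endoscopy or X-ray with water soluble contrast or both at the discretion of an investigator". Tables 8A and 8B both mark POD 1 endoscopy as optional, and neither has an X-ray row.
- **Disclosure.** Section 9d: "At 6 months, all patients will be informed about their treatment allocation". The 6M visit consists of symptom questionnaires and body weight/BMI.

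**The concern.** In a sham-controlled trial with a symptom score as the primary endpoint, the inference depends on patients not knowing their arm. By the plan's own standard one cue is unmatched: a puncture through the abdominal wall can follow a myotomy taken to the serosa, but has no place in a plain endoscopy. A G-POEM patient who notices the mark may infer the allocation within a day of the procedure and report symptoms accordingly for six months.

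The second gap is the more lasting one. Perceived allocation is never recorded, and after disclosure at 6 months it cannot be recovered. This is data collection, so no later analysis plan can supply it. A reader who asks whether belief contributed to the result could not be answered from the data.

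**Working it through.** **1. Cues side by side**

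| Element | G-POEM | Sham | Matched? |
|---|---|---|---|
| Intravenous PPI, antibiotics | Active drug | Saline | Yes |
| Nil by mouth to POD 1 | Yes | Yes | Yes |
| Oral PPI from POD 1 | Yes | Yes | Yes |
| EndoFLIP at 3M (window 3–9 months) | Measured | Sham measurement | Yes |
| POD 1 endoscopy (Tables 8A, 8B) | Optional | Optional | Same entry |
| Abdominal decompression | If necessary | Nothing described | No |

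**2. Search for a record of belief.** I looked at the 3M, 6M, 12M, 24M and 36M visit lists (section 9d), Tables 8A and 8B, and the GCSI, PAGI-SYM and PAGI-QoL as reproduced in Appendices 2 and 4. None contains a treatment-guess question. Pages withheld from the public text could not be checked.

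**3. The plan's own sample size.** Inputs from section 11: 50% v 20%, significance level 0.05 (taken as two-sided), power 0.80, drop-out 15%. With unpooled variance:

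n = (0.25 + 0.16) × (1.960 + 0.842)² / 0.30² = 35.8, so 36 per arm.

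36 / (1 − 0.15) = 42.4, so 43 per arm and 86 in total. This reproduces the stated figure, and 36 per arm is used below.

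**4. Illustration of size (assumed inputs).** Assume no true effect, with 20% success in both arms. A share f of G-POEM patients recognise their arm, and their chance of reporting success rises by b. The apparent G-POEM rate is then 20% + f × b.

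- f = 20%, b = 10 points: 20 + 2 = 22%
- f = 20%, b = 20 points, or f = 40%, b = 10 points: 20 + 4 = 24%
- f = 40%, b = 20 points: 20 + 8 = 28%

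Rejection probability is the sum of Bin(x; 36, p₁) × Bin(y; 36, 0.20) over all pairs (x, y) for which the pooled two-proportion |z| exceeds 1.96:

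| G-POEM v sham | Two-sided rejection |
|---|---|
| 20% v 20% | 4.9% |
| 22% v 20% | 5.4% |
| 24% v 20% | 6.7% |
| 28% v 20% | 12.2% |

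In the last row, 11.9 of the 12.2 points favour G-POEM. The pooled test stands in for the planned regression. The protocol states neither f nor b.

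**The case against.** **The masking is already substantial, and the cue is narrow.** Decompression happens only when needed, its frequency is not given, and nothing says that a patient would see the mark or understand it. At the low end of the illustration the error rate moves only from 4.9% to 5.4%. All of this stands, and it limits the point to a cheap improvement. It does not answer the absence of any record of belief.

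**A reader might infer that Table 8B lets sham patients miss the POD 1 leak test, so that the test itself reveals the arm.** The documents do not support that. Table 8A, "study design for patients in the active (G-POEM) group", carries the same optional entry as Table 8B, "study design for patients randomized in the sham group". Endoscopy is naturally optional where contrast X-ray may be used instead, and section 8 already requires the same post-procedure tests in the sham arm. What remains is an incomplete schedule: there is no X-ray row, and the remark about closing the incision fits only G-POEM.

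**A reader might also suppose that large shares of both arms would recognise their allocation, which would give a much larger error rate.** Neither the puncture nor the POD 1 schedule supports this for the sham arm. Having no puncture tells a sham patient little when decompression is only occasional, so the illustration is confined to G-POEM patients.

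**Analysing the endpoint by guess would be imprecise.** That is correct. Three answer categories within about 36 patients per arm leave small groups, so such an analysis can only be descriptive.

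**Conclusion.** The point holds in limited form. One arm-related physical cue has no sham counterpart, although the plan masks its other perioperative steps. Perceived allocation is not collected before disclosure, so the success of masking cannot be assessed for the only confirmatory endpoint. It would go too far to conclude that blinding failed or that the result is biased: the documents contain no evidence on either.

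The size is unknown. Under the assumed ranges (20–40% of G-POEM patients recognising their arm, reporting success 10–20 points more often, 36 per arm, 20% true success in both arms), the false-positive rate rises from 4.9% to 5.4–12.2%. The lower end is negligible and the upper end is not. The design is not invalidated, but the remedy is cheap and the missing information cannot be rebuilt later.

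**What to change.** - **Match the cue.** Apply the same small abdominal dressing to every patient in both arms before waking. This is a masking measure and leaves the decision on decompression untouched.
- **Record belief.** Add one question (G-POEM / sham / don't know) at discharge and again at the 6M visit, after the symptom questionnaires and before allocation is disclosed.
- **Report it.** Tabulate the answers by arm, with the discharge answer as the main one. Present any breakdown of the primary endpoint by guess as descriptive only.
- **Minor clarification.** Make Tables 8A and 8B consistent with sections 8 and 9c, including the X-ray option, so that it is plain that POD 1 testing does not depend on the arm.

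The cost is a short amendment, one dressing per patient and one question at two existing contacts. The drawback is that the 6M guess is influenced by symptom change, which is why the discharge answer should carry the interpretation. For patients already told their arm the information is lost. If enrolment has closed, as the monitoring board's letter recommends, the trial report should say that masking was not assessed.
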